## STUDY PROTOCOL

Interested subjects will contact the study via the contact information provided in the study advertisement. [name], [name], or their research assistant(s) will then contact each potential subject by phone (or by each subject's preferred method of communication) in order to set up a brief phone interview, during which the requirements for the study will be reviewed. [name], [name], or their research assistant(s) will then perform the initial phone screening to verify that subjects meet the criteria specified in the advertisement. The Recruitment Script Phone will be used for note taking during the call, but the sheet is then shredded after the call and the information is recollected when the subject arrives for her/his screening visit (if eligible), and after they provide signed informed consent. If a prospective subject is a staff under the supervision of either [name] or [name], the supervising individual will not participate in the recruitment process in order to avoid potential coercion or undue influence. In addition, UCB students, in general, will be routinely screened (initial phone screening) by research assistants, rather than by faculty.

For subjects who state that they are potentially eligible for enrollment, we will arrange an initial visit, at the subject's convenience, to perform further screening and to gather initial behavioral data. The Subject Health screening sheets will be filled out immediately (and only) after obtaining written informed consent. The Tolcapone package insert will be shared with subjects to inform them of possible side effects. Consent will be obtained only at approved sites for this study, including either the subject suite in the UC Berkeley Imaging Center (BIC) or the clinic and testing rooms at the UCSF Research Clinic. Subjects will read through the consent form prior to signing the document; if for some reason a subject is unable to read the form, the consenting study investigator will read the forms to the subject. Subjects will be provided as much time as required for them to familiarize themselves with the contents of the consent form. Any questions the subject has concerning the contents of the consent form, or the consent process itself, will be answered prior to signing. Only after informed consent is obtained will the remainder of the initial visit, described below, be completed.

We will administer an extensive questionnaire listing contraindications to MRI scanning. Because the MRI scanner attracts certain metals, subjects who may have metallic objects in their bodies will be excluded. (As an additional measure of protection, we will use a hand-held metal detector to screen subjects before entering the scanner.)

Subjects will provide a saliva sample in order to determine catechol-O-methyltransferase (COMT) and dopamine receptor subtype 2 (DRD2) genotypes. DNA extraction and analysis will be conducted using standard methods to assess the Val158Met polymorphism of the COMT gene and the A1+ polymorphism in the DRD2 gene. Examiners and researchers who interact with study subjects or study data will remain blinded to genotype until the end of the study. Furthermore, genes affecting dopamine metabolism in addition to COMT and DRD2 will be examined (including the dopamine transporter variable number tandem repeat (DAT VNTR) and dopamine receptor subtype 4 single nucleotide polymorphism 521 (DRD4 SNP-521)). In order to further assess potential contraindications to tolcapone, a blood sample will be tested for routine chemistries including white cell count, red cell count, platelet count, hemoglobin, hematocrit, mean cell volume (MCV), mean cell hemoglobin (MCH), mean cell hemoglobin concentration (MCHC), red cell distribution width (RDW), mean platelet volume (MPV), neutrophils, lymphocytes, monocytes, eosinophils, and basophils. Additionally, because of potential hepatic effects of tolcapone, a hepatic screen will assay total protein, albumin, globulin, A/G ratio, bilirubin (total, direct, and indirect), alkaline phosphatase, aspartate aminotransferase

(AST, aka serum glutamic oxaloacetic transaminase (SGOT)), and alanine aminotransferase (ALT, aka serum glutamic pyruvic transaminase (SGPT)). Elevation of plasma bilirubin, AST (SGOT), ALT (SGPT), or alkaline phosphatase greater than 3 times normal values will be grounds for subject exclusion. (Note that ongoing monitoring of liver enzymes will not be necessary, as only a single, counterbalanced dose of tolcapone will be administered to each subject.) The blood sample may also be used for genetic testing if the saliva sample is non-diagnostic, compromised, or otherwise unavailable. Tests for blood chemistries following phlebotomy are currently performed at Quest Diagnostics in Berkeley, CA or the main laboratory at UCSF.

Subjects will then be urine-screened for illicit drug use (Biotechnostix) and screened for intoxication via breathalyzer (Lifeloc Technologies). To confirm that subjects do not have potential drugs of abuse in their system, an on-site rapid urine-screening and a breathalyzer test will be done before administering tolcapone or placebo. Urine-screening will be done via an integrated test cup that includes a temperature sensor. The drug classes detected include cocaine, amphetamine, methamphetamine, tetrahydrocannabinol (THC), and opiates. Additionally, two opiates (methadone and oxycodone) may not be reliably detected by the 5-Test Integrated cup, so urine dipstick screening (Innovacor, Inc.) will also be performed on each subject's urine sample for these two

compounds. These drugs have been chosen due to their possible interaction with tolcapone and their possible cognitive and cardiovascular effects. No identifiers will be put on the test cup and it will be read immediately and discarded by the researcher. Similarly, the results of the breathalyzer will be read and then the test will be discarded. Moreover, due to the potentially sensitive nature of this information, the results will not be written down. Subjects who test positive for any of these substances will be excluded from further participation in the study. Subjects will also be excluded if they regularly use medications that affect dopamine levels, or will have used these medications within two weeks of tolcapone administration (including tolcapone, except as part of our study, or any of the following: levodopa/carbidopa, entacapone, amantadine, pergolide, pramipexole, ropinirole, selegiline, isocarboxazid, phenelzine, tranylcypromine, clozapine, olanzapine, quetiapine, risperidone, ziprasidone, aripiprazole, fluphenazine, haloperidol, perphenazine, pimozide, thiothixene, trifluoperazine, loxapine, molindone, chlorpromazine, mesoridazine, thioridazine, dextroamphetamine, dexmethylphenidate, or methylphenidate).

A licensed health care provider listed in the protocol will also conduct a brief physical exam. This exam will search for signs of medical illness, including jaundice or abdominal distension associated with liver disease, that would exclude subjects from participating in the study. (See exclusion criteria.) For the purposes of the exam, female subjects will not be limited to a female provider, and male subjects will not be limited to a male provider. However, our practice has been, and will continue to be, that a research subject may always request a male or female provider. If for some reason the requested provider is not available, a member of the research team of the requested gender can also be present for the exam, if desired.

Female subjects will also be screened for pregnancy, as the effects of the study drug during pregnancy are not adequately known and the drug may appear in breast milk. Since subjects may not know they are pregnant, all female subjects recruited to participate in the study will be required to have a urine pregnancy test prior to each session of the study. They will self-administer the test after coming into the research lab. These pregnancy tests have been in

reliable use at the UC Berkeley Brain Imaging Center for approximately 10 years without any reported failures. Subjects will be provided with printed instructions in the use of the test.

Active use of substances other than alcohol or tobacco, use of alcohol on the day of the meeting as assessed by breathalyzer testing, and/or a positive pregnancy test, will be grounds for exclusion.

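### Does leaving drug and breathalyzer results unwritten, with no rule for subjects who have only one session, undermine the analysis?

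*Combined protocol and SAP*

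**What the plan says.** Under the STUDY PROTOCOL heading, the text says that "an on-site rapid urine-screening and a breathalyzer test will be done before administering tolcapone or placebo". The reason for the panel is given: "These drugs have been chosen due to their possible interaction with tolcapone and their possible cognitive and cardiovascular effects". The consequence is also given: "Subjects who test positive for any of these substances will be excluded from further participation in the study". A later paragraph in the same section lists, among the grounds for exclusion, "use of alcohol on the day of the meeting as assessed by breathalyzer testing". The test cup carries no identifier, both tests are read and discarded, and "due to the potentially sensitive nature of this information, the results will not be written down".

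Two other statements bear on the number of sessions. Female subjects "will be required to have a urine pregnancy test prior to each session of the study", and the liver-monitoring note says that "only a single, counterbalanced dose of tolcapone will be administered to each subject". Together they imply a paired tolcapone and placebo session for each subject, although the text never says so directly. The protocol does keep some screening paperwork: "The Subject Health screening sheets will be filled out immediately (and only) after obtaining written informed consent".

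The STATISTICAL ANALYSIS PLAN covers sample size and power only. It plans to recruit at least 35 subjects in each of three arms and claims at least 88% power for a behavioral effect size of 0.5 at the 0.05 level in a 2x2 ANOVA with group and drug as factors. It states no analysis set, attrition allowance or missing-session rule.

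**The concern.** The screened substances may interact with the study drug and may affect cognition, so the tests protect the behavioral outcome as well as the subject. If nothing is stored, a passed test and a forgotten test leave the same trace. With 3 x 35 = 105 subjects and two dosing sessions each, that could apply to as many as 210 sessions. A subject lost after the first session could not be classed as an eligibility failure or as some other loss.

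The SAP then appears to compound this. A conventional repeated-measures ANOVA drops any subject with one missing session, and the plan does not say whether that is intended. Nor does it say whether 35 per arm means recruited or evaluable subjects. At stake would be the credibility of the eligibility gate, some precision, and a choice of analysis set left until after the data are seen.

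**Working it through.** **What the no-record rule covers.** Its object is the results. It does not forbid a generic entry that the subject was eligible to proceed. The text describes no such entry, but the public text is incomplete on this point: it refers to exclusion criteria that it does not reproduce and to health screening sheets whose content it does not show. Clearance is therefore not described, which is weaker than not documented.

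**What recorded results would add to the analysis.** Under the protocol's own rules, every subject who proceeds has passed. Among analysed sessions the recorded value would be constant, so it could not act as a covariate or change an estimate. Its use would be in audit. The number of one-session subjects is visible from the session data in any case.

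**Size of the one-session question.** Inputs from the SAP: 35 per arm, effect size 0.5, alpha 0.05, power at least 88%. Assumptions, because the documents are silent: the group factor compares two arms (N = 70), 0.5 is in units of the SD of the within-subject difference, tests are two-sided, losses are 10, 20 or 30%, and the between-session correlation rho is 0.3 to 0.7.

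*The plan's own figure.* Power comes from the noncentral t distribution.
- Drug effect in one arm: noncentrality 0.5 x √35 = 2.96, df 34, power 82% (89.5% one-sided).
- Drug main effect in two arms: 0.5 x √70 = 4.18, df 68, power 98.5%.
- Group-by-drug interaction: 0.5 x √(35/2) = 2.09, df 68, power 54.1%.

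The 88% is not uniquely reproduced, because the SAP does not say which effect or which effect-size metric it means.

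*Complete pairs only*, with evaluable numbers rounded down per arm:

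| Assumed loss | Pairs per arm | Drug main effect, two arms | Drug effect, one arm | Interaction |
|---|---|---|---|---|
| 0% | 35 | 98.5% | 82.0% | 54.1% |
| 10% | 31 | 97.2% | 76.8% | 49.1% |
| 20% | 28 | 95.7% | 72.3% | 45.1% |
| 30% | 24 | 92.4% | 65.0% | 39.6% |

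The two-arm main effect stays at or above 88% down to 21 pairs per arm.

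*Keeping the single sessions in a mixed model.* A complete pair carries information 1/[2σ²(1 − rho)] on the drug effect. With balanced orders, a single session carries 1/(4σ²). The ratio is (1 − rho)/2, which is 0.35 at rho 0.3 and 0.15 at rho 0.7. With C pairs and L single-session subjects, the variance falls by the fraction wL/(C + wL), where w is that ratio. Taking C and L from N = 70 directly:
- 10% loss (C = 63, L = 7): 1.05/64.05 = 1.6% to 2.45/65.45 = 3.7%.
- 20% loss (C = 56, L = 14): 2.1/58.1 = 3.6% to 4.9/60.9 = 8.0%.
- 30% loss (C = 49, L = 21): 3.15/52.15 = 6.0% to 7.35/56.35 = 13.0%.

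So the mixed model recovers 15 to 35% of the information that the losses remove. For the interaction at 30% loss and rho 0.3, the effective number per arm is 24 + 11 x 0.35 = 27.85, close to the 28-per-arm row. Power would be about 45% instead of 39.6%.

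**The case for a change.** The strongest case for a change is that the gate and its silence are explicit, and the remedy is cheap. One pooled entry per session, eligible to proceed or not, would show that the checks were done without naming a substance. Dosing alone does not prove that a test took place. The pregnancy test is expressly tied to every session and the drug and alcohol tests are not, so their timing is left to inference. A missing-session rule takes one line and is best fixed before data are seen.

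Most of this stands as good record-keeping. It does not show a faulty plan. The rule is a deliberate choice with a stated privacy reason, and the recruitment paragraph shows that the pool may include university students and staff supervised by the investigators, for whom a stored result carries real risk. Even a pooled entry keeps some of that risk, and it would still not give the reason for an exclusion.

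The two halves are also only loosely connected. If the drug and alcohol tests are done once, at the first visit, they create no one-session subjects. If they are repeated, nothing in the text suggests that failing one depends on which treatment came first. The remaining losses are ordinary attrition. For them, a mixed model trades a small gain in precision for a missing-at-random assumption, and statisticians can reasonably differ on that trade. Declaring that the quoted power refers to 35 evaluable subjects would assert something the SAP does not say.

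**Conclusion.** No change to the plan follows. The unwritten results are a fair trade-off between privacy and audit, and they alter no estimate: testing and exclusion go ahead as described, and a site can keep a generic eligibility note without departing from the text. The timing of the tests and the one-session rule are missing details. Reading the tests as done before each administration, and analysing either complete pairs or all available sessions, are both sensible ways to fill them.

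The choice between the two analyses is worth 1.6 to 3.7% of the drug-effect variance at 10% loss and up to 13.0% at 30% loss. These figures rest on assumed loss rates, an assumed correlation of 0.3 to 0.7, balanced orders and losses that all follow the first session. The power figures further assume that two arms form the group factor, except in the one-arm column. One-arm and interaction power fall more than the two-arm main effect, but interaction power is only 54.1% with no loss at all. That is a question about the basis of the 88% figure and is separate from record-keeping and missed sessions. A documented high loss rate, or evidence that loss depends on treatment order, would reopen the point; the documents contain neither.

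### Does tying the two-week medication window to tolcapone alone leave the placebo session screened on different terms?

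*Combined protocol and SAP*

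**What the plan says.** The medication rule in the STUDY PROTOCOL section has two limbs. The first has no session anchor: "Subjects will also be excluded if they regularly use medications that affect dopamine levels". The second catches more recent, not necessarily regular, use: subjects are out if they "will have used these medications within two weeks of tolcapone administration". A list of drugs follows, and tolcapone itself is on it unless it was given within this study.

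The rules nearby are worded for both conditions. For drugs of abuse and alcohol, "an on-site rapid urine-screening and a breathalyzer test will be done before administering tolcapone or placebo". Women repeat the pregnancy test before every session. Being an active user of any substance apart from alcohol and tobacco is also grounds for exclusion, with no reference to either treatment.

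On design, the protocol says that "only a single, counterbalanced dose of tolcapone will be administered to each subject". The STATISTICAL ANALYSIS PLAN section crosses group with drug in a 2x2 ANOVA. The paragraph on the physical exam refers to a separate list of exclusion criteria, which is not part of the text available here.

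**The concern.** Placebo is the comparator for the drug factor. If recent use of a dopamine-acting drug is barred before tolcapone but not before placebo, background medication could differ between the two levels of that factor. Counterbalancing would not cure this: it balances order, whereas this rule follows the treatment.

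The contrast with the neighbouring wording makes the omission look meaningful, since the authors named both conditions when they described the urine screen. Their reason for choosing the urine-tested drugs also reaches placebo in part: "These drugs have been chosen due to their possible interaction with tolcapone and their possible cognitive and cardiovascular effects". Interaction with tolcapone matters only when tolcapone is given, but a drug's own cognitive effect matters in either session. At stake would be a biased tolcapone-placebo difference, and a biased group-by-drug interaction if such use were more common in one group.

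**Working it through.** The plan states no figure on this point, so there is none to reproduce. The check has three parts.

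**1. How much of the pre-placebo period the literal window misses.** Take the tolcapone session as day 0 and the placebo session g days before or after it. The documents do not give g, so it is an assumption, varied from 1 to 28 days. Count how many of the 14 days before placebo lie outside the window.

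- *Window read as the two weeks before tolcapone.* Uncovered days = min(g, 14), in either order. For g = 7 this is 7; for g = 14 or more it is all 14.
- *Window read as two weeks on either side, placebo first.* Again min(g, 14).
- *Window read as two weeks on either side, placebo second.* Uncovered days = min(max(g − 14, 0), 14). This is 0 up to g = 14, then 21 − 14 = 7 at g = 21 and 28 − 14 = 14 at g = 28.

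So on a literal reading some days are missed in at least one order for any g of 1 or more.

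**2. Who could fall into the gap.** Regular users are excluded by the first limb, at any session. What remains is a person who does not regularly use a listed drug but takes one near placebo and outside the tolcapone window. The urine cup is only a weak backstop: "The drug classes detected include cocaine, amphetamine, methamphetamine, tetrahydrocannabinol (THC), and opiates". Of the 30 list entries besides tolcapone (levodopa/carbidopa counted once), one, dextroamphetamine, matches a urine class by name. The exclusion for active substance use has no tolcapone anchor and could catch some of the rest, but the term is not defined.

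**3. What the clause itself suggests.** Each subject receives one study dose of tolcapone. If the window were only the two weeks before that dose, the dose could not fall inside it, and excepting it would do nothing for this limb. The exception does real work if the window also precedes a placebo session that comes second. It could instead simply keep the study dose from counting against the subject, for instance under the two-sided reading, so it is a pointer and not proof.

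**Size.** The bias would depend on how many subjects took a listed drug near placebo only and on how far their scores moved. The documents give neither. The list mixes drugs that enhance dopamine with drugs that block it, so even the sign is open. A percentage of the planned effect of 0.5 would rest on invented inputs, and the plan does not say what units that 0.5 is in. I give no such figure.

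**The case for a change.** The best case for acting is that the text is clear and the repair is a few words. The window names tolcapone only, nothing else in the available text sets one for placebo, and the existence of a second limb shows that the authors thought occasional use worth excluding. Nor can one simply rely on screeners being unaware of treatment order, because the only blinding stated is to genotype: "Examiners and researchers who interact with study subjects or study data will remain blinded to genotype until the end of the study".

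The literal gap stands, and so does the silence on treatment blinding in this text. The consequence does not follow from either. The available text is short, and the exclusion criteria it refers to may already settle the point. A tolcapone anchor can also be coherent if the list is meant as a check on contraindications: the protocol introduces the blood tests in that spirit and gives no reason for the medication list. Which anchor is right is for the sponsor; the statistical question is only whether results would be unsound if the plan were followed as written. Nothing in the documents suggests that they would be.

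**Conclusion.** No change to the plan follows. The wording is looser than that of the rules around it, and asking which session or sessions the window refers to is a fair editorial query. It is not a flaw in the design or the analysis. Regular use is barred throughout, the urine and breath screens cover both treatments, and the exception for study tolcapone points towards a window meant for both sessions. Staff running a counterbalanced placebo comparison would sensibly fill the gap by asking about recent medication before each one.

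The effect on the tolcapone-placebo contrast cannot be sized from the documents. It is zero if no such use occurs or if the window is applied to both sessions. No stated sample size, power or significance level is affected.

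This rests on two assumptions: that occasional use of the listed drugs is rare among people who are not regular users, and that the separate exclusion criteria do not deliberately permit it before placebo. Evidence against either would reopen the question.

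### The protocol gives possible passage of the drug into breast milk as a reason for screening women, but the steps it describes would not identify a breastfeeding woman who is not pregnant

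*Combined protocol and SAP*

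**What the plan says.** The paragraph on pregnancy screening in the STUDY PROTOCOL section says why women are screened: "as the effects of the study drug during pregnancy are not adequately known and the drug may appear in breast milk". That is two hazards, one to a pregnancy and one to a nursing infant. The procedure that follows is that "all female subjects recruited to participate in the study will be required to have a urine pregnancy test prior to each session of the study". Subjects carry out the test themselves at the research lab.

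The section ends with a short list of exclusion grounds (substance use, alcohol on the day, pregnancy). The reproductive item reads "and/or a positive pregnancy test, will be grounds for exclusion". Breastfeeding is not mentioned there, and the reason given for the screen is the only place in the available text where breast milk appears.

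On exposure, the paragraph on blood tests says that "only a single, counterbalanced dose of tolcapone will be administered to each subject".

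**The concern.** A screen should be able to detect each condition it is meant to guard against. This one names two hazards and acts on one. A pregnancy test says nothing about lactation, and the exclusion tied to it depends only on the test result. A woman nursing an infant and not pregnant would test negative and stay eligible under the rule as written.

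What is at stake is the safety of an infant who is not a participant and cannot consent, exposed to a drug that the protocol itself says may be present in milk. With one dose per subject, the women who matter are those breastfeeding around the time of that dose. The described procedure does not identify them.

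**Working it through.** The plan gives no figure on this point and no arithmetic applies. The check is to take a hypothetical subject, a woman who is breastfeeding, not pregnant and otherwise healthy, through each step in the STUDY PROTOCOL section and ask whether the text as written would stop her.

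**Steps whose content is described**

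- *Saliva sample.* Used for dopamine-related genotypes. It does not bear on breastfeeding.
- *Blood sample.* Blood counts and a hepatic screen. The exclusion is for liver values "greater than 3 times normal values will be grounds for subject exclusion". She passes.
- *Urine drug screen and breathalyzer.* "Subjects who test positive for any of these substances will be excluded from further participation in the study". She passes.
- *Medication rule.* Excludes users of drugs that act on dopamine. She passes.
- *Physical exam.* Described as a search for medical illness, with signs of liver disease as the examples. Breastfeeding is not an illness and is not mentioned. She passes.
- *Urine pregnancy test.* Negative, because she is not pregnant. She passes.
- *Closing exclusion sentence.* None of its grounds applies to her. She passes.

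**Steps that are named but whose content is not available**

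- *Advertisement criteria and phone script.* The phone screen checks the former and uses the latter. Neither is reproduced.
- *Subject Health screening sheets.* Completed after consent. The questions are not reproduced.
- *MRI questionnaire.* Described as a list of contraindications to scanning, with the stated rule that "subjects who may have metallic objects in their bodies will be excluded". Its full content is not reproduced.
- *Exclusion criteria.* The exam paragraph refers to findings "that would exclude subjects from participating in the study. (See exclusion criteria", so a separate list exists. The list itself is not reproduced. The pointer belongs to illness found at the exam; the pregnancy and breast-milk paragraph has no pointer of its own.

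**Information given to subjects**

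- *Package insert and consent form.* The insert is shared to describe side effects. The consent pages were removed from the text before review. Neither is described as an eligibility check.

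Result: no step whose content is described would stop this subject. Five named sources (exclusion criteria, advertisement, phone script, Subject Health sheets, MRI questionnaire) could stop her, but whether any does cannot be determined. If none does, she could receive one tolcapone dose while breastfeeding.

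**The case against.** The strongest reply is that the exclusion may sit in a document that was not available. The text refers to separate exclusion criteria and to health sheets, and the procedures described here are plainly not the full eligibility section: age limits and inclusion criteria are absent too. The silence of this text on one more criterion is weak evidence about the trial as a whole. That stands, and it limits the claim.

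A second reply is that the paragraph concerns testing. It explains the test by the fact that a woman may be unaware of a pregnancy. Breastfeeding is known to the woman, so it needs a question and not a test, and a health history form is the natural place for one. On this reading the breast-milk clause is a loosely attached rationale. This is plausible but cannot be confirmed from the text. It also supports the remedy, since it concedes that a question is the right tool.

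A reader might infer that the trial admits breastfeeding women, or that it has no breastfeeding exclusion anywhere. The documents do not support either statement. They show only that the stated step and the stated exclusion do not serve one of the two stated reasons. None of the available text closes that gap.

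**Conclusion.** The point holds in a limited form. The protocol names breast milk as a hazard, and the screening step and exclusion it describes do not act on it. A breastfeeding woman who is not pregnant would pass every step whose content is described and could be dosed.

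The size is small and partly unknown. Exposure is at most one tolcapone dose per woman. The documents give neither the number of female subjects nor how many might be breastfeeding, so no count is offered. If any of the five unavailable sources already excludes breastfeeding, the trial's exposure from this route is nil. Infant exposure is therefore possible but not shown.

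The conclusion rests on two assumptions: that a urine pregnancy test does not detect breastfeeding, and that the described steps are applied as written. No endpoint, sample size or analysis depends on it. It is best classed as a cheap improvement in patient safety.

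**What to change.** Ask each female subject at the screening visit whether she is currently breastfeeding. Information from the phone screen is already collected afresh at that visit after consent, so the question fits there. Ask again alongside the pregnancy test before the dosing session. Because that test already precedes every session, the repeat covers the tolcapone session whichever order the subject is assigned.

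Amend the closing exclusion sentence so that its reproductive ground reads: a positive pregnancy test or current breastfeeding.

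The cost is one question at contacts that already take place and a few words in one sentence, with no added test, visit or staff. The downside is the loss of very few otherwise eligible women.
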